6.2 Primary Endpoints

The primary endpoints of this registry are below, based on different points in time:

Perioperative endpoint-

1. Technical success, defined as ablation of the target lesion(s) according to the protocol and covered completely, with an adequate margin, as defined by the performing physician (i.e. the ablation zone completely overlaps or encompasses the target lesion(s) plus an ablative margin), as assessed by CT, MRI, PET, US, and/or X-ray, immediately following the procedure.

Short term endpoint-

2. Technique efficacy, ablation of the target lesion(s) according to the protocol and covered completely, with an adequate margin, as defined by the performing physician (i.e., the ablation zone completely overlaps or encompasses the target lesion(s) plus an ablative margin), as assessed by CT, MRI, PET, US, and/or X-ray, at Visit 3 (between 7 days and less than 3 months post-ablation).

Long term endpoint-

3. Target lesion recurrence (local recurrence) rate evaluated at every visit after ablation of the target lesion(s), and overall evaluation at the 5-year follow-up, as assessed by CT, MRI, PET, US, and/or X-ray.

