17.9 Analyses to be Conducted

Categorical variables will be summarized descriptively by frequencies and associated percentages. Continuous variables will be summarized descriptively by number of patients, mean, standard deviation, median, minimum, and maximum. Confidence intervals will also be provided for procedure-related variables.

Disposition of Registry Patients

Patient disposition will be summarized using counts and percentages. The number and percentage of patients completed and discontinued along with the specific reasons for discontinuation will be tabulated.

Demographic and Baseline Characteristics

Summary statistics will be provided for patient demographics and pre-operative ablation characteristics.

Primary and Secondary Endpoint Analyses

Regression analysis methodologies will be utilized to explore the relationship between dichotomous clinical outcomes (technical success, technique efficacy, and secondary efficacy rate) and ablation procedure, patient, and provider parameters. Time to event analyses will be used for target lesion recurrence, regional recurrence rate, recurrence-free survival, progression free survival, and overall survival.

Complete details regarding all analysis methodologies including approaches to handle multiple lesions per patient, variable selection techniques, data reduction techniques given the number of potential independent variables, as well as subgroup analyses of interest will be specified in the SAP.

The number and percentage of patients achieving technical success will be summarized and a 95% confidence interval will be provided. A similar summary will be provided for technique efficacy, as well as for the primary and secondary efficacy rates, as previously defined.

Target lesion recurrence rates at each post-ablation scheduled visit will be estimated using the Kaplan-Meier method and 95% confidence intervals will be provided. A similar summary will be provided for the 5-year overall rate. Similar summaries will also be provided for regional recurrence rate, overall and progression-free survival rates for the entire observation period from the ablation procedure date through 5 years of follow-up.

Scores from the EORTC QOL questionnaires and Numeric Pain Rating Scales will be summarized with methodology consistent to the recommendations of the specific survey. Additional endpoints will be summarized with descriptive statistics.

Plans for Interim Analysis

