1.2 Study Design

This is a multicenter, observational registry that follows patients for a total of up to 5 years from the date of the first liver ablation procedure with either the NEUWAVE Microwave Ablation System or the NEUWAVE Microwave Ablation System with Ablation Confirmation.

This is an “umbrella registry,” which was included as an optional component in other NEUWAVE studies; hence, data from consenting patients who are or will be enrolled in other NEUWAVE soft tissue liver lesion ablation studies will be included in this registry. All other patients will be enrolled and followed prospectively, enrolled retrospectively with prospective, longitudinal follow up, or enrolled retrospectively with all retrospective follow up.

2 Treatment Assignment

This is a single-arm registry where all enrolled patients will be ablated using the NEUWAVE Microwave Ablation System as part of the site’s SOC treatment or per protocol for those patients who are also enrolled in other NEUWAVE studies.

3 Randomization and Blinding Procedures

As this is a single-arm registry, no randomization will occur, and no blinding procedures are required.

4 Interval Windows

Interval windows are provided in the Schedule of Assessments section of the study protocol. No additional windows are planned for analysis purposes.

5 Levels of Significance

No levels of significance are specified as no specific hypotheses about any of the outcomes of interest are being formulated or tested. Two-sided 95% confidence intervals (CI) will be estimated for specific endpoints for descriptive purposes only.

6 Analysis Sets

All Enrolled Set (AES): Consists of subjects who signed informed consent form or retrospectively enrolled with a waiver for signing informed consent form. The AES will be used for disposition of study subjects.

Full Analysis Set (FAS): FAS Consists of subjects who met inclusion/exclusion criteria and to whom the NeuWave Ablation device was utilized during procedure. Primary and secondary endpoints will be analyzed using FAS.

Safety Analysis Set (SAF): SAF Consists of subjects who met inclusion/exclusion criteria and to whom the NeuWave Ablation device was utilized during procedure. Safety endpoints will be analyzed using SAF.

7 Sample Size Justification

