8.4.1 Primary Endpoint

Perioperative endpoint-

1. Technical success, defined as ablation of the target lesion(s) according to the protocol and covered completely, with an adequate margin, as defined by the performing physician (i.e., the ablation zone completely overlaps or

encompasses the target lesion(s) plus an ablative margin), as assessed by CT, MRI, PET, US, and/or X-ray, immediately following the procedure. Technical Success is assessed at Visit 2 following the ablation of the target lesion.

Short term endpoint -

2. Technique efficacy, ablation of the target lesion(s) according to the protocol and covered completely, with an adequate margin, as defined by the performing physician (i.e., the ablation zone completely overlaps or encompasses the target lesion(s) plus an ablative margin), as assessed by CT, MRI, PET, US, and/or X-ray, at Visit 3 (between 7 days and less than 3 months post-ablation).

Long term endpoint -

3. Target lesion recurrence (local recurrence) rate evaluated at every visit starting from visit 4 after the primary ablation at visit 2 of the target lesion(s), and overall evaluation at the 5-year follow-up, as assessed by CT, MRI, PET, US, and/or X-ray.

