8.5 Analysis of Primary Endpoint

The number and percentage of patients and lesions achieving technical success will be summarized and a two-sided 95% confidence interval will be provided based on Clopper-Pearson's method. Technical success is achieved when the ablation is defined as a complete ablation by the performing physician. Technical success will be summarized at patient level and at lesion level. Technical success is achieved for a patient when all ablated lesions are defined as a complete ablation by the performing physician.

The number and percentage of patients and lesions achieving technique efficacy will be summarized and a two-sided 95% confidence interval will be provided based on Clopper-Pearson's method. Technique efficacy is achieved when the ablation is defined as a complete ablation by the performing physician. Technique efficacy will be summarized at patient level and at lesion level. Technique efficacy is achieved for a patient when all ablated lesions are defined as a complete ablation by the performing physician.

Target lesion recurrence will be summarized at patient level and at lesion level. Time-to-event analysis (survival analysis) using Kaplan-Meier's method will be utilized to estimate the target lesion recurrence rate at 3-month, 6-month, up to 60-month follow up. Cumulative incidence rate will be estimated for target lesion recurrence considering death as a competing risk and estimates will be presented at 3-month, 6-month, up to 60-month follow up. A two-sided 95% CI will be estimated for target lesion recurrence. Subjects who failed technique efficacy will be excluded from the analysis for target lesion recurrence.

First occurrence of a target lesion recurrence at patient level will be considered as the “event” for time-to-event analysis.

First occurrence of a target lesion recurrence at lesion level will be considered as the “event” for time-to-event analysis.

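### The planned 3-month target lesion recurrence estimate is structurally about 0% if events are dated at the scan, because the SAP evaluates recurrence only from Visit 4, whose window opens at 3 months

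*SAP*

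**What the plan says.** Target lesion recurrence is the long-term primary endpoint. SAP 8.5 uses Kaplan-Meier to "estimate the target lesion recurrence rate at 3-month, 6-month, up to 60-month follow up". It adds a cumulative incidence estimate "considering death as a competing risk and estimates will be presented at 3-month, 6-month, up to 60-month follow up". Before either analysis, it removes subjects who failed technique efficacy. SAP 8.4.1 places that evaluation "at Visit 3 (between 7 days and less than 3 months post-ablation".

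SAP 8.4.1 defines the recurrence endpoint as a "rate evaluated at every visit starting from visit 4 after the primary ablation at visit 2". The Schedule of Assessments gives Visit 4 as 3 to <6 months, and SAP section 4 says "No additional windows are planned for analysis purposes".

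The protocol differs in two respects:

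- Protocol 6.2 has "Target lesion recurrence (local recurrence) rate evaluated at every visit after ablation of the target lesion(s", and the schedule marks recurrence evaluation at Visit 3.
- Protocol 17.9 ties the estimates to visits, not months: "Target lesion recurrence rates at each post-ablation scheduled visit will be estimated using the Kaplan-Meier method".

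SAP 8.5 defines the event as the first recurrence. It does not say whether event time is the scan date or a nominal visit time, what the time origin is, how months convert to days, or whether an unscheduled scan before Visit 4 counts.

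**The concern.** A time-to-event estimate at 3 months is informative only if an event can be recorded by 3 months. Here the first qualifying scheduled evaluation falls in a window that opens at 3 months. The one earlier scheduled scan, Visit 3, belongs to a different endpoint, and its failures are excluded.

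A primary-endpoint table would then show a 3-month local recurrence of about 0% with an interval of no width. A reader would take this as a finding about the device when it is a product of the counting rule. SAP 8.8 repeats the analysis by disease type and by use of the ablation confirmation software, so every subgroup would show the same zero and look alike. SAP 8.7 plans no sensitivity analysis that would reveal it.

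The SAP's handling of regional recurrence suggests an oversight. SAP 8.6 uses the same time points there but counts events from Visit 3, including unscheduled visits, so its 3-month estimate can differ from zero.

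**Working it through.** The plan states no recurrence rate for this endpoint, so there is no figure of its own to reproduce. The check has three parts.

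**1. Windows against the 3-month time point** (Schedule of Assessments; SAP 8.4.1, 8.5)

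| Visit | Window | Counts for target lesion recurrence in the SAP? |
|---|---|---|
| 3 | 7 days to <3 months | No: technique efficacy; failures excluded |
| 4 | 3 to <6 months | Yes: first qualifying visit |
| 5 | 6 to <9 months | Yes |
| 14 | 54 to 60 months | Yes |

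With scan-dated events, the number of scheduled events before 3 months is d = 0.

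- Kaplan-Meier: S(3) is the product of (1 − d/n) over event times up to 3 months. With no events S(3) = 1, so the recurrence rate is 1 − 1 = 0%.
- Cumulative incidence: the sum of S(t−) × d/n over recurrence times up to 3 months is also 0, whatever the number of deaths.
- Greenwood variance: S² × Σ d/[n(n − d)] = 0, so the interval is 0 to 0.

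**2. What the true rate could be**

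These assumptions are not from the documents: constant hazard; 12-month recurrence p of 5%, 10% or 20%; Visit 3 scan uniform between 0.25 and 3 months; lesions already recurrent at that scan excluded; no deaths or dropout.

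Hazard per month: λ = −ln(1 − p)/12.

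True 3-month rate among included lesions: 1 − exp(−3λ)/E, where E = [exp(−0.25λ) − exp(−3λ)]/(2.75λ) is the probability of passing Visit 3.

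| p | λ | exp(−3λ) | E | True 3-month rate | Planned estimate |
|---|---|---|---|---|---|
| 5% | 0.00427 | 0.98726 | 0.99308 | 0.6% | 0% |
| 10% | 0.00878 | 0.97400 | 0.98586 | 1.2% | 0% |
| 20% | 0.01860 | 0.94574 | 0.97034 | 2.5% | 0% |

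A simulation of 400,000 lesions under the same assumptions gave 0.58%, 1.20% and 2.50% for the true rate, and 0.0% for the planned estimate each time. Weighting scans towards the start of each window also gave 0.0%.

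**3. What could make the estimate differ from zero**

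- *Opening-day scans.* A positive scan at exactly 3 months counts. If Visit 4 scan days are uniform over 92 days, 1/92 = 1.1% of scans fall on that day. In the extreme case where every Visit 4 scan falls then (with Visit 3 at 1 month), the simulated estimate is 0.8% to 3.6% across the three values of p.
- *Early unscheduled scans.* Protocol 12.4 allows recurrence imaging at any unscheduled visit. SAP 8.5 does not bar such events, but SAP 8.4.1 read literally starts at Visit 4.
- *Visit-coded time.* If each visit takes the month its window opens, Visit 4 is month 3, but Visit 14 is month 54 and no visit matches the planned 60-month estimate. If each takes the month its window closes, Visit 14 is month 60, but month 3 is then Visit 3, where recurrence is not evaluated.

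**The case against.** The strongest objection is that the zero depends on a convention the SAP does not state. Protocol 17.9 speaks of rates at scheduled visits. Under visit-coded time the 3-month label could mean Visit 4, and the estimate would not be zero. The table shells are in a separate document and may settle this. A reader might therefore infer too much in saying that the estimate must be 0% by construction: scan dating is an assumption, an opening-day scan counts, and early unscheduled scans are not clearly excluded. That stands, and the finding is limited accordingly. It does not clear the plan, because neither simple way of coding visits to months fits both the 3-month and the 60-month estimates, and no mapping is given.

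The harm is also bounded. No hypothesis is tested, the intervals are descriptive, and incomplete ablations seen at Visit 3 are reported as technique efficacy, itself a primary endpoint. This limits the consequence but does not make the 3-month figure informative.

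A reader might go on to infer that the 6- and 12-month estimates are wrong because they leave out later scans. The documents do not support that. They attach no month label to any visit, SAP 8.5 does not name 12 months, and the Visit 7 window is not printed. Visit 6 closes at 12 months and Visit 14 at 60, so scans in those windows fall within the estimates at those times. Any shortfall against true recurrence is ordinary detection delay under standard-of-care imaging. Reporting at the end of a window uses the same scans and would leave it unchanged.

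**Conclusion.** The point holds in this limited form. With scan-dated events, the planned 3-month Kaplan-Meier and cumulative incidence estimates are about 0% with a degenerate interval, overall and in each subgroup, because no scheduled evaluation can supply an earlier event. The size depends on assumption: about 0% would be reported against a true 0.6% to 2.5% if 12-month recurrence is 5% to 20%, under constant hazard and uniform scan timing. The absolute error is small; the problem is a primary-endpoint figure that carries almost no information about the device.

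Two further points do not depend on those assumptions. The SAP's Visit 4 start contradicts Protocol 6.2 and the schedule, and the SAP defines neither the event time nor the link between months and visits. The later time points are not shown to be in error.

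**What to change.** 1. In SAP 8.5, delete the 3-month target lesion recurrence estimate for both estimators. Alternatively, count as events recurrences found after a complete technique-efficacy evaluation and before Visit 4, including at unscheduled scans. Deletion is cleaner: with one scheduled scan before 3 months, the added events would come largely from off-schedule imaging.
2. State that event time is the date of the first positive scan, measured from the ablation date. Give the month-to-day conversion and the rule for unscheduled scans before Visit 4.
3. Tie each remaining estimate to a named visit window, as Protocol 17.9 asks.
4. Reconcile the SAP's Visit 4 start with Protocol 6.2 and the schedule, keeping technique-efficacy failure distinct from recurrence. Carry the decision into the recurrence-free survival definition in SAP 8.6, which also starts its target lesion component at Visit 4.

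The cost is SAP wording and table-shell labels, with a protocol clarification if the Visit 4 start is kept. No new data are needed.

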9. If applicable, per site SOC: genetic markers include Alpha-fetoprotein (AFP), Carbohydrate antigen 19-9 (CA19-9), Carcinoembryonic antigen (CEA)
10. Record all relevant prior medications taken within 60 days prior to Visit 2 and all relevant concomitant medications taken throughout the registry. Relevant concomitant medications include: chemotherapy, immunotherapy, blood-thinning or coagulation, NSAIDs, those medications used to treat AEs, those used for hepatitis (if concurrently treating), and any others that are relevant in the opinion of the investigator. For post-ablation follow-up visits, relevant concomitant medications may be assessed over the phone, as needed.
11. Quality of Life questionnaires: EORTC QLQ-C30 and liver-specific QLQ-HCC18. The questionnaires may be administered over the phone, as needed.
12. Pain score, using the Numeric Pain Rating Scale. The questionnaire may be administered over the phone, as needed.
13. Use SOC imaging for all study visits.
14. Ablation procedure details, as listed in Section 19.1 of the protocol.
15. Healthcare provider parameters, as listed in Section 19.1 of the protocol.
16. SOC imaging as used at every follow-up visit to determine if there is local or regional recurrence of lesion(s). If there is a recurrence, determine soft tissue lesion details, via CT, MRI, PET, US, and/or X-ray. Scans will be submitted to the Sponsor (refer to NOTE 1).
17. Record only relevant concomitant procedures (i.e. liver or lesion-related). For post-ablation follow-up visits, relevant concomitant procedures may be assessed over the phone, as needed.
18. Technical success, defined as ablation of the target lesion(s) according to the protocol and covered completely, with an adequate margin, as defined by the physician performing the ablation (that is, the ablation zone completely overlaps or encompasses the target lesion plus an ablative margin), as assessed by CT, MRI, PET, US, and/or X-ray, immediately following the procedure. If patient has had any lesions ablated with NeuWave in the post-ablation follow-up visit period, assess Technical success following each ablation.
19. Technique efficacy, defined as ablation of the target lesion(s) according to the protocol and covered completely, with an adequate margin, as defined by the physician performing the ablation (that is, the ablation zone completely overlaps or encompasses the target lesion plus an ablative margin), as assessed by CT, MRI, PET, US, and/or X-ray, at Visit 3.

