8.6 Analysis of Secondary Endpoints

The number and percentage of patients and lesions achieving secondary efficacy will be summarized and a two-sided 95% confidence interval will be provided based on Clopper-Pearson’s method. Analysis for secondary efficacy rate includes only repeat ablations for target and non-target lesions.

For patient level analysis – secondary efficacy is achieved for a patient when all re-ablations of target lesions and all re-ablations of non-target lesions are defined as a complete ablation by the performing physician. The denominator for subject level analysis will include subjects who had a re-ablation during visit 3 to visit 14 including unscheduled visits.

For lesion level analysis – secondary efficacy is achieved for a lesion when all repeat ablations of that lesion (target and non-target lesions) are defined as complete ablation by the performing physician. The denominator for lesion level analysis will include lesions that had a repeat ablation during visit 3 to visit 14 including unscheduled visits.

Regional recurrence rates will be estimated at patient level. Time-to-event analysis (survival analysis) using Kaplan-Meier’s method will be utilized to estimate the regional recurrence rate at 3-month, 6-month, up to 60-month follow up. Two-sided 95% CI will be estimated for regional recurrence rate. First occurrence of identification of a new lesion outside the initial treatment site(s) during visit 3 to visit 14 including unscheduled visits at patient level will be considered as the “event” for time-to-event analysis at patient level.

Recurrence-free survival rates will be estimated at patient level. Time-to-event analysis (survival analysis) using Kaplan-Meier’s method will be utilized to estimate the recurrence-free survival rate at 3-month, 6-month, and up to 60-month follow up. Two-sided 95% CI will be estimated for recurrence-free survival rate.

An “event” is defined for recurrence-free survival if any of the following conditions are met:

- a. First occurrence of a target lesion recurrence during visit 4 to visit 14 including unscheduled visits at patient level
- b. Identification of a new non-target lesion during visit 3 to visit 14 including unscheduled visits at patient level

c. Deaths from any cause of a patient during the follow up period

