8.10 Exploratory Analyses

Logistic regression analysis will be utilized to explore the relationship between dichotomous clinical outcomes (technical success and technique efficacy) and ablation procedure, patient, and provider parameters. Significance level of 0.2 will be used for variable selection in a regression model. Cox proportional hazard model will be used for time to event analyses for target lesion recurrence to explore the relationship with ablation procedure, patient, and provider parameters.

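### Recurrence-free survival keeps patients with local failure at Visit 3 but does not count that failure as an event, and the recurrence exclusion is worded by subject even at lesion level

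*SAP*

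**What the plan says.** **Target lesion recurrence.** SAP 8.5 gives one exclusion sentence for both the patient-level and the lesion-level analysis: "Subjects who failed technique efficacy will be excluded from the analysis for target lesion recurrence". Technique efficacy is judged at Visit 3, and at patient level one incomplete lesion is enough to fail: "Technique efficacy is achieved for a patient when all ablated lesions are defined as a complete ablation by the performing physician". SAP 8.4.1 has the recurrence "rate evaluated at every visit starting from visit 4 after the primary ablation at visit 2". Protocol 6.2 sets no such start; its endpoint reads "Target lesion recurrence (local recurrence) rate evaluated at every visit after ablation of the target lesion(s".

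**Recurrence-free survival.** SAP 8.6 defines the local component as "First occurrence of a target lesion recurrence during visit 4 to visit 14 including unscheduled visits at patient level". The other two components are a new non-target lesion from Visit 3 onwards and death from any cause. SAP section 6 assigns secondary endpoints to the FAS, and SAP 8.6 removes nobody for technique failure. SAP 8.4.2 and Protocol 6.3 both have this endpoint evaluated at all visits following ablation, with no Visit 4 start.

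**Visits.** In the protocol's Schedule of Assessments, Visit 3 runs from 7 days to <3 months and Visit 4 from 3 to <6 months. The schedule marks a recurrence evaluation at Visit 3 as well as the technique efficacy evaluation. SAP 8.7 plans no sensitivity analyses.

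**The concern.** A patient whose treated lesion shows viable tumour or local recurrence at Visit 3 is handled in two different ways. For target lesion recurrence the patient leaves the analysis. For recurrence-free survival the patient stays in the risk set, but the finding is not an event. A patient with a new lesion elsewhere in the liver at the same visit does have an event. No reason is given for the difference.

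The recurrence-free survival curve is then too high, most of all in the first months. The subject-level wording also affects lesion-level recurrence, where patients with several lesions lose successfully treated lesions because another lesion failed.

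**Working it through.** The documents state no expected technique efficacy, recurrence or survival rate, so there is no planned figure to reproduce. Every rate below is an assumption.

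**1. Trace of a local failure at Visit 3**

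| Endpoint | Treatment of the patient | Source |
|---|---|---|
| Target lesion recurrence | excluded | SAP 8.5 |
| Recurrence-free survival | at risk, no event at Visit 3 | SAP 6, 8.6 |
| Regional recurrence | not an event (only lesions outside the treated sites count) | SAP 8.6 |
| Overall survival | not an event | SAP 8.6 |

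The finding is an event in none of the four time-to-event endpoints. It is reported through the binary technique efficacy endpoint. Secondary efficacy counts re-ablations from Visit 3 onwards (SAP 8.6). A patient re-ablated for a Visit 3 finding can therefore be a secondary efficacy success and never have a recurrence-free survival event.

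**2. Size for recurrence-free survival**

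Let f be the share of patients with local failure at Visit 3. Let S0 be recurrence-free survival among the rest at a given time. Let q be the share of the Visit 3 failures who have a counted event by that time.

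- SAP rule: (1-f)S0 + f(1-q)
- Visit 3 failure counted: (1-f)S0
- Overstatement: f(1-q), which does not depend on S0

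With S0 = 70% at 12 months (assumed):

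| f | Counted | SAP rule, q=30% | q=50% | q=80% | Overstatement (points) |
|---|---|---|---|---|---|
| 5% | 66.5% | 70.0% | 69.0% | 67.5% | 3.5 / 2.5 / 1.0 |
| 10% | 63.0% | 70.0% | 68.0% | 65.0% | 7.0 / 5.0 / 2.0 |

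The q=30% column gives Visit 3 failures the same later risk as everyone else (1-S0 = 30%), which is unlikely with residual tumour. It is best read as the upper end.

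**3. Lesions lost from lesion-level recurrence**

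Assume 65/22/9/4% of patients have 1/2/3/4 lesions (mean 0.65+0.44+0.27+0.16 = 1.52) and that lesions fail independently with probability 5%. A completely ablated lesion in a patient with k lesions is dropped with probability 1-0.95^(k-1), that is 0, 0.05, 0.0975 and 0.1426 for k = 1 to 4.

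(0.44×0.05 + 0.27×0.0975 + 0.16×0.1426) / 1.52 = 0.0711/1.52 = 4.7% of good lesions.

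**4. The 3-month estimate**

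SAP 8.5 plans target lesion recurrence estimates from 3 months on. Visit 3 failures are excluded and events start at Visit 4, which opens at 3 months. No event can fall before then, so an estimate at month 3 is essentially zero by construction. Recurrence-free survival at month 3 reflects only new non-target lesions and deaths.

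**5. Total local failure beside conditional recurrence**

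With r the recurrence rate among technique successes and deaths ignored, total local failure is f+(1-f)r. For f=8% and r=15% this is 0.08+0.92×0.15 = 21.8%. The plan would report the 8% and the 15%, but not their combination.

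**The case against.** **Conditional recurrence is a legitimate estimand.** Recurrence presupposes a complete ablation, and the SAP states the exclusion openly. A reader might infer that the plan hides Visit 3 failures or reports a falsely low recurrence rate. The documents do not support that: technique efficacy is itself a primary endpoint, reported per patient and per lesion with confidence intervals. The 21.8% and the 15% above are different quantities. This objection stands, and it leaves a need for a label and a supportive table.

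**Visit 3 failures are not permanently event-free.** A reader might infer that they count as recurrence-free survivors throughout. They stay at risk and can have a target lesion recurrence recorded from Visit 4, a new lesion, or death. The SAP does not say whether tumour persisting at Visit 4 is a first occurrence, or whether an unscheduled finding before Visit 4 counts. Hence the result is a range over q. The objection limits the size but does not remove the inconsistency.

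**The Cox model.** SAP 8.10 says a "Cox proportional hazard model will be used for time to event analyses for target lesion recurrence". If it is fitted on the restricted set, it conditions on an outcome of the same ablation parameters, and a reader might infer bias towards no effect. That is not shown. SAP 8.10 does not restate the exclusion, selection of this kind can act in either direction, and the same section plans logistic regression of technique efficacy on those parameters. The result is conditional, and no direction of bias follows.

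**Wording.** Protocol 17.9 plans estimates at each scheduled visit, so the SAP's 3-month time point may be only a label for Visit 4. The subject-level exclusion may be loose drafting. Both are possible, and both need saying in the SAP.

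**Conclusion.** The inconsistency in recurrence-free survival is real and follows from the text alone. SAP 8.6 neither excludes technique failures nor counts their local failure when it is found, contrary to SAP 8.4.2 and Protocol 6.3. The direction is optimistic. The size is f(1-q): 1.0-3.5 points at f=5% and 2.0-7.0 points at f=10% for q between 30% and 80%, all assumed.

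Three lesser points stand with it. The Visit 4 start for target lesion recurrence departs from Protocol 6.2. The exclusion as worded costs about 5% of completely ablated lesions under the assumptions in step 3; no resulting bias in the lesion-level rate has been shown. A true month-3 recurrence estimate carries no information.

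This should be fixed, but it does not undermine the registry, which is single-arm, tests no hypotheses and uses its confidence intervals descriptively.

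**What to change.** 1. In SAP 8.6, count incomplete ablation or local recurrence at Visit 3 as a recurrence-free survival event, dated at the Visit 3 imaging. State that an unscheduled finding before Visit 4 is handled in the same way.
2. In SAP 8.5, exclude only the failed lesion from lesion-level target lesion recurrence.
3. Label target lesion recurrence as conditional on technique efficacy, reconcile its Visit 4 start with Protocol 6.2, and drop the 3-month estimate or relabel it as Visit 4.
4. Add one supportive table in the FAS: cumulative incidence of total local failure (Visit 3 failure or later target lesion recurrence), with death as a competing risk.
5. In SAP 8.10, state the analysis set of the Cox model. If it is the restricted set, describe the results as conditional on technique efficacy and present them beside the logistic model of technique efficacy. Replacing the Cox outcome is not required.

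The cost is SAP wording and one extra table from data already collected. Reported recurrence-free survival will be somewhat less favourable.
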